Primary and Secondary Safety Endpoints. The FAVoR intervention will be interspersed with the care team’s activities, and at no time will the study personnel delay or interfere with critical care procedures; if the needs and activities of providers are such that the study personnel are unable to access the subject to provide audio reorientation, the subject will be withdrawn from the study. At all times, we will place the subject’s need for medical treatment, and avoidance with interference with treatment, foremost.

To reduce skin irritation from applied devices, the Sleep Profiler and ActiWatch will not be placed on skin that is not intact or damaged in any way. The Sleep Profiler and ActiWatch will be removed as soon as data collection is complete (up to 120 hours) and skin assessments will be conducted daily. If the skin shows any signs of irritation, the sleep monitoring devices will be discontinued.

If a 20% or larger fluctuation in vital signs (heart rate and blood pressure) during the recorded message occur, research staff will turn off the recorded message. The clinical nurse assigned to the subject will be immediately notified, and the clinical medical provided will be notified as well. The message will be restarted when the critical care nurse or physician indicates the patient is stable. If the 20% or larger fluctuation in vital signs re-occurs, the intervention will be discontinued and the in-hospital data only up to that point will be included in the study.

Prior to beginning the NIH Toolbox Cognition Battery testing and questionnaires, the subject will be told if they feel excessively frustrated or anxious during the test, they may stop. There is no alternative therapy. However, subjects may elect not to participate and may withdraw from the study at any time without affecting the care they receive.

IRB Study Number: 20170771, Version #1.8, Date: 03/10/21, PI: [name]

9. Procedures Involved

Research Design

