2) minimizing research-associated risk: We anticipate minimal additional physical and psychological risks associated with this study. Reorientation is routinely provided to critically ill patients by bedside nurses as part of clinical care. The intervention will be interspersed with the care team's activities, and at no time will the study personnel delay or interfere with clinical care; if the needs and activities of providers are such that the study personnel are unable to access the subject to provide interventions, the subject will be withdrawn from the study. At all times, we will place the subject's need for medical treatment, and avoidance with interference with treatment, foremost. Because these subjects are receiving clinical care in the hospital, the attending clinical nursing and medical providers will be promptly informed of any adverse effects to the subjects; if an adverse event occurs, necessary interventions will be determined and delivered by the clinical providers.

3) protecting the confidentiality of participant data: In order to reduce risks to privacy of individuals or confidentiality of data, we will not include personally identifiable data in the

IRB Study Number: 20170771, Version #1.8, Date: 03/10/21, PI: [name]

database files. All computers and data files will be password protected, and data will be stored on the University server, with access only to study personnel, under the direct supervision of the PI, [name]. Each subject will be assigned an arbitrary code number to conceal the identity of the research data, and no identifiable private information will be associated with any data files. All data will be collected on laptops in the clinical setting; these laptops will remain in the possession of study personnel at all times (unless locked in a cabinet in the locked research office), and all study-related files will be password protected. At the conclusion of each segment of the subject's participation (ICU, hospital discharge, 1 month post-hospital, 6 months posthospital), that subject's data will be transferred from the laptop computer to a secure, password protected file on the UM server, under the direct supervision of [name], with access limited to study personnel. Study information obtained will be kept strictly confidential, and it will not be possible to identify any participant from the reports that may result from this research.

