- Stop collecting research data.
- Remove all research equipment.
- Mail Thank You card with \$25 gift card to subject’s home address. □ Redact PHI from Enrollment Tracking Log.

In the event the subject (or their LAR) withdraws from the study, we will consider the study complete for the subject and use all information collected up to the point of study withdrawal. The same study completion procedures above will be followed.

13. Risks to Subjects

The risks of participation in the study are minimal. Risks of the intervention may include transient changes in vital signs from stimulation caused by the recorded message. Other risks include skin irritation from the actigraphy watch and sleep profiler-polysomnography, as well as frustration or anxiety with the NIH Toolbox Cognition Battery testing or any of the questionnaires (see Table 1). None of these risks were observed to occur in preliminary study #2.

Following consent and study enrollment, risk of breach of confidentiality is also possible since identifying information will be collected in an electronic enrollment tracking list, on a password

IRB Study Number: 20170771, Version #1.8, Date: 03/10/21, PI: [name]

protected server limited to project director and research assistants, to track the location of subjects as inpatients and contact information for follow up home visits.

There is no alternative therapy. However, subjects may elect not to participate and may withdraw from the study at any time without affecting the care they receive.

Protections Against Risk

The FAVoR intervention will be interspersed with the care team's activities, and at no time will the study personnel delay or interfere with critical care procedures; if the needs and activities of providers are such that the study personnel are unable to access the subject to provide audio reorientation, the subject will be withdrawn from the study. At all times, we will place the subject's need for medical treatment, and avoidance with interference with treatment, foremost.

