If a 20% or larger fluctuation in vital signs (heart rate and blood pressure) during the recorded message occur, research staff will turn off the recorded message. The clinical nurse assigned to the subject will be immediately notified, and the clinical medical provided will be notified as well. The message will be restarted when the critical care nurse or physician indicates the patient is stable. If the 20% or larger fluctuation in vital signs re-occurs, the intervention will be discontinued and the in-hospital data only up to that point will be included in the study.

IRB Study Number: 20170771, Version #1.8, Date: 03/10/21, PI: [name]

Prior to beginning the NIH Toolbox Cognition Battery testing and questionnaires, the subject will be told if they feel excessively frustrated or anxious during the test, they may stop. There is no alternative therapy. However, subjects may elect not to participate and may withdraw from the study at any time without affecting the care they receive.

As of March 2020, per the updated guidance regarding research continuity from the University of Miami IRB and research administrations, we are complying with the COVID-19 safety recommendations to protect our subjects, research personnel, students, and faculty members.

14. Potential Benefits to Subjects

Subjects in the intervention group may benefit from this study if delirium is reduced by the FAVoR intervention. The data obtained will provide empirical evidence that will enable us to evaluate the effect of the FAVoR intervention on delirium and holds promise to translate new knowledge into clinical decision-making about the management of delirium in the critically ill to ultimately improve patient outcomes.

15. Vulnerable Populations

Cognitively Impaired Adults

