In our experience in conducting clinical research in the critical care areas, we have found that potential subjects who are mechanically ventilated are generally sedated to some degree. In addition, since use of mechanical ventilation primarily occurs during periods of patient instability, the use of sedation at these times is extensive and compromises patient's ability to communicate effectively which is compounded by the presence of the endotracheal tube. As a result, we have always found it appropriate to contact the legally authorized representative for consent. However, there may be rare occurrences when potential subjects are adequately oriented and lucid to be able to provide informed consent. Therefore, we will use the 2-step procedure described by Fan et al.⁷⁶ to determine the patient's ability to provide informed consent. Step 1 is objective evaluation with the Richmond Agitation-Sedation Scale (RASS) and the Confusion Assessment Method for Intensive Care Unit (CAM-ICU). Patients who score -1, 0, +1 on the RASS indicating drowsy, alert, or restless respectively and are not delirious (CAM-ICU = No) will move to Step 2. Step 2 is assessment for competency using the MacArthur Competence Assessment Tool for Clinical Research: MacCAT-CR that evaluates all four capacity domains for consent (understanding, appreciation, reasoning, expression of a choice). Evaluation of Step 1 requires approximately 2-3 minutes, Step 2 requires approximately 15 minutes. Fan et al.⁷⁶ found in consent evaluations of 150 ICU patients that 89% were sedated/delirious, and unable to provide consent; our experience in previous research is similar. Therefore, we expect that few potential subjects will move to Step 2 while critically ill and mechanically ventilated. The LAR will be contacted for those who fail Step 1 or Step 2.

We will evaluate the potential subject's level of orientation and response to our discussions of the study on a daily basis during the hospital phase, and if the potential subject is able to respond in a manner that is clearly understandable, we will use the potential subject's own consent to continue participation. However, in any instance where the potential subject's ability to comprehend and communicate his/her desires is in question, we will seek consent for continued participation from the LAR and will invite the research subject to provide his/her assent.

IRB Study Number: 20170771, Version #1.8, Date: 03/10/21, PI: [name]

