Subjects will be withdrawn if they appear to be unduly distressed. For example, if a 20% or larger fluctuation in vital signs (heart rate and blood pressure) during the delivery of the recorded message occur, research staff will turn off the recorded message. The clinical nurse assigned to the subject will be immediately notified, and the clinical medical provider will be notified as well. The message will be restarted when the critical care nurse or physician indicates the patient is stable. If the 20% or larger fluctuation in vital signs re-occurs, the intervention will be discontinued and the in-hospital data only up to that point will be included in the study.

Verbal consent to continue participation and for post-hospital follow up will be obtained from the subject as soon as their medical condition permits. We will follow UM IRB, JMH, and UMH policies and procedures. The consenting process for Spanish patients, family members, and/or LAR's will be the same process only with the addition of an individual UMH or JMH Spanish translator or by use of the UMH translation language line phone service, which is available 24 hours a day, 7 days a week.

Pregnant Women

This minimal risk study carries no added risk to pregnant women and the well-being of their unborn child.

16. Sharing of Results with Subjects

Individual subject results will not be shared with subjects or others (i.e., health care providers) during the study. De-identified study group results will be made available through publications and summarized on clinicaltrials.gov.

17. Setting

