Following IRB approval of the partial HIPAA waiver, the trained Project Director or RAs will review the potential subject's medical record, and if there are no exclusions, the subject will be invited to enroll. The subject and the subject's LAR will be provided with an oral explanation of the nature of the study and study information, in writing. The information will include all elements required for informed consent, and will include all pertinent contact information as well as information about withdrawal from the study. Written consent will be obtained if the consent process is conducted in person. If the LAR is contacted by phone or HIPAA compliant Zoom, review of the consent forms will be completed over the phone or by Zoom by the Project Director or RAs, as is done in person. Verbal consent will be obtained over the phone or by Zoom. Waiver of wet signature will be documented by the person obtaining consent.

If at any time the subject or LAR does not wish to continue to participate in the study, no additional interactions with the subject will take place, no follow-up data will be collected and that subject's data forms will be destroyed. [name] (study PI) has extensive experience in obtaining consents from family members of critically ill adults. The study staff will work closely with the staff of the Cardiac Care, Medical, Neuro, Surgical, and Specialty ICUs, nurse managers, and medical directors to ensure that all eligible patients have an equal opportunity for inclusion.

In our experience in conducting clinical research in the critical care areas, we have found that potential subjects who are mechanically ventilated are generally sedated to some degree. In addition, since use of mechanical ventilation primarily occurs during periods of patient instability, the use of sedation at these times is extensive and compromises patient's ability to communicate effectively which is compounded by the presence of the endotracheal tube. As a result, we have always found it appropriate to contact the legally authorized representative for consent. However, there may be rare occurrences when potential subjects are adequately oriented and lucid to be able to provide informed consent. Therefore, we will use the 2-step procedure described by Fan et al.⁷⁶ to determine the patient's ability to provide informed

IRB Study Number: 20170771, Version #1.8, Date: 03/10/21, PI: [name]

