Subjects will be withdrawn if they appear to be unduly distressed. For example, if a 20% or larger fluctuation in vital signs (heart rate and blood pressure) during the delivery of the recorded message occur, research staff will turn off the recorded message. The clinical nurse assigned to the subject will be immediately notified, and the clinical medical provider will be notified as well. The message will be restarted when the critical care nurse or physician indicates the patient is stable. If the 20% or larger fluctuation in vital signs re-occurs, the intervention will be discontinued and the in-hospital data only up to that point will be included in the study.

Verbal consent to continue participation and for post-hospital follow up will be obtained from the subject as soon as their medical condition permits. We will follow UM IRB, JMH, and UMH policies and procedures. The consenting process for Spanish patients, family members, and/or LAR's will be the same process only with the addition of an individual UMH or JMH Spanish translator or by use of the UMH translation language line phone service, which is available 24 hours a day, 7 days a week.

Adults Unable to Consent

In our experience, potential subjects who are critically ill, especially during the first 48 hours of intubation, are always sedated to some degree, and their ability to communicate effectively is compromised by endotracheal intubation; for these reasons, permission for the subject's participation has generally been obtained from the LAR. Upon the initial screening of the medical record for eligibility, we will review the medical record for any named health care surrogate or a court appointed guardian. If neither of these are named, the following order of potential LARs will be assessed: spouse, adult child, parent, adult sibling, adult relative, a close friend, or a clinical social worker.

We will evaluate the potential subject's level of orientation and response to our discussions of the study on a daily basis during the hospital phase, and if the potential subject is able to respond in a manner that is clearly understandable, we will use the potential subject's own consent to continue participation. However, in any instance where the potential subject's ability to comprehend and communicate his/her desires is in question, we will seek consent for continued participation from the LAR and will invite the research subject to provide his/her assent.

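### A recurrent 20% vital-sign fluctuation, possible only in the FAVoR arm, cuts off the post-ICU assessment and leaves the 1- and 6-month visits unsettled

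*Combined protocol and SAP*

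**What the plan says.** The vital-sign rule appears five times: in section 8 (Primary and Secondary Safety Endpoints), section 13 (Protections Against Risk), section 15 (Cognitively Impaired Adults), and twice in section 26 (Cognitively Impaired Adults; Adults Unable to Consent).

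The steps are the same each time. At a first fluctuation of 20% or more during a message, staff switch the message off and notify the nurse and provider. Then: "The message will be restarted when the critical care nurse or physician indicates the patient is stable". If it happens again, "the intervention will be discontinued and the in-hospital data only up to that point will be included in the study".

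The versions in sections 15 and 26 carry an extra lead-in: "Subjects will be withdrawn if they appear to be unduly distressed. For example, if a 20% or larger fluctuation in vital signs". Sections 8 and 13 do not have it.

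Elsewhere, withdrawal means leaving the study. When providers' activities leave staff "unable to access the subject to provide interventions, the subject will be withdrawn from the study" (section 11; sections 8 and 13 are similar). Section 12 completion procedures begin with "Stop collecting research data". Section 26 says that once the subject or LAR does not wish to continue, "no additional interactions with the subject will take place, no follow-up data will be collected".

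Section 9 says both groups have cognitive and health-status evaluations at three times: as an inpatient at least 24 hours after ICU discharge, then as an outpatient at 1 and 6 months after hospital discharge.

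**The concern.** The trigger is tied to the playing of a message. A FAVoR subject can hear up to 40 messages and a control hears none, so the rule acts on one arm only, after randomisation, in response to a reaction to the intervention.

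Secondary aim 3 compares the arms on cognition and health status after the ICU and at 1 and 6 months. Dropping those assessments for FAVoR subjects who react means the comparison no longer covers everyone as randomised. For the post-ICU assessment the plan already does this. For the two later visits it may, depending on how staff read the withdrawal lead-in.

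The analysis plan offers little protection. Part I says in general terms that missing data may be imputed, and it sets out multiple imputation for the primary outcome. The aim 3 path models in Part II name no missing-data method.

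A mistaken withdrawal could also be hard to reverse. Section 12 completion includes redacting identifying details from the enrolment tracking log, and section 13 says that log holds the contact information for the home visits.

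**Working it through.** The plan states no figure for this rule, so the main check is a comparison of text.

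| Place | Messages stop on recurrence | In-hospital data cut at that point | Given as an example of withdrawal |
|---|---|---|---|
| Section 8 | yes | yes | no |
| Section 13 | yes | yes | no |
| Section 15 | yes | yes | yes |
| Section 26, Cognitively Impaired Adults | yes | yes | yes |
| Section 26, Adults Unable to Consent | yes | yes | yes |

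**Post-ICU assessment.** Section 9 places it in hospital. After a recurrence it is in-hospital data past the cut, so all five versions exclude it. This does not depend on the lead-in.

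**1- and 6-month visits.** The cut-off sentence has two readings. Either only the in-hospital data are truncated and outpatient follow-up goes on, or nothing is used except in-hospital data before the recurrence. Other text does not decide between them:
- Section 12 covers imminent death and withdrawal by the subject or LAR. It does not list this event.
- The no-follow-up statement in section 26 applies when the subject or LAR does not wish to continue.
- Section 9 says both groups are followed up, without mentioning this event.
- The monthly progress report in section 11 has no category for messages stopped early with follow-up continuing.
- The study manual promised in section 18 might settle it, but it is not among the documents.

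**Reach of the withdrawal wording.** It sits under cognitively impaired adults and adults unable to consent, which is most of the sample. The protocol cites a study in which "89% were sedated/delirious, and unable to provide consent; our experience in previous research is similar". If that share held here, 0.89 × 91 = 81 of 91 FAVoR subjects would be covered.

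**Size.** Inputs from the plan: 91 per arm and 40% attrition (section 8), and 8 messages a day for 5 days (section 9). The recurrence rate f is assumed.
- Exposure: 8 × 5 = 40 messages at most per FAVoR subject, 0 per control.
- Expected completers per arm: 91 × 0.6 = 54.6, about 55.
- Subjects with a recurrence, 91 × f: 1.8 at 2%, 4.6 at 5%.
- Completers lost, 55 × f: 1.1 at 2%, 2.8 at 5% (assuming recurrence is unrelated to other attrition). Controls lost: 0.
- Chance that the rule is met at least once among 91, 1 − (1 − f)^91: 0.60 at 1%, 0.84 at 2%, 0.99 at 5%.
- Illustrative shift in the FAVoR mean, f × d, where d is the difference between lost and retained subjects. With d assumed anywhere from −1 to +1 SD, the shift is within ±0.02 SD at 2% and ±0.05 SD at 5%.
- Standard error of a difference with 55 per arm: √(2/55) = 0.19 SD. So 0.05/0.191 = 0.26, about a quarter of a standard error.

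**What the pilot adds.** Section 13 says none of the listed risks occurred in the 30-subject pilot, in which 20 subjects heard messages. For 0 of 20, the one-sided 95% upper limit is 1 − 0.05^(1/20) = 13.9%, or about 13 of 91. The pilot fits a low rate but does not establish one.

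**The case against.** The best defence is that the procedure is identical in all five places and only an introductory sentence differs. After that sentence, the specific text says what happens: pause, restart, then stop the intervention. A first event clearly withdraws nobody. The procedures that end follow-up are written for other triggers. Limiting the cut to in-hospital data also fits continued outpatient follow-up. And the effect touches a secondary aim for which 40% attrition is already planned.

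Much of this stands. A reader might infer that sections 8 and 13 merely stop the messages and that the trouble lies only in sections 15 and 26. The documents do not support that, because sections 8 and 13 carry the same data cut. A reader might also infer that the protocol orders follow-up to end after a recurrence. It does not say so; the withdrawal reading is possible, not established.

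What the defence does not remove is the stated exclusion of the post-ICU assessment, or the silence on the two later visits. Wording that merely fits continued follow-up does not tell staff to carry it out.

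**Conclusion.** The point holds in two parts. After a recurrence, the plan as written excludes the inpatient post-ICU assessment, in the FAVoR arm only. Whether the 1- and 6-month visits continue is not settled, and the withdrawal wording in sections 15 and 26 allows them to end, again in one arm only.

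The effect is probably small: about 1-3 of roughly 55 FAVoR completers against 0 controls, at a recurrence rate of 2-5%. That rate is an assumption, as is the ±1 SD range behind the illustrative shift. It would be tempting to say that the rule flatters FAVoR by removing subjects who react badly. The documents do not link this reaction to later cognition or health status, so they support no direction of bias.

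The change is worth making because the loss is avoidable, confined to one arm, and cheap to prevent. The same cut-off sentence also reaches CAM-ICU ratings taken after a recurrence; that effect is not sized here.

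**What to change.** - In section 15 and in both places in section 26, remove the vital-sign event as an example of subject withdrawal.
- In all five places, replace the sentence that limits in-hospital data. Removing the lead-in alone would leave the post-ICU assessment excluded and the later visits ambiguous. Suggested rule: *A recurrence stops the messages only. Section 12 completion procedures are not triggered. The subject stays in the randomised arm, and all planned post-ICU, 1-month and 6-month assessments are collected and analysed unless the subject or LAR withdraws.*
- Keep the pause, notification and restart steps, and withdrawal by the subject or LAR, as they are.
- Report the number of subjects whose messages were stopped under this rule.

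The cost is protocol wording in four sections. The visits are already planned. The downside is a few more assessments in subjects whose messages were stopped.
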